The proposed research is specifically designed to investigate the ability of a novel tool to identify atypically developing infants from their typically developing peers. There will be an initial portion for usability feedback of hardware and software. For testing: For the first portion of the study (Part A) we will recruit up to 10 infants for analysis for up to two sessions each. After this initial testing, twenty-four infants will be recruited to participate, including 12 who are developing typically and 12 who are identified as at-risk for neuromotor delay. Infants with typical development will be at least 3 months and less than 11 months of age, score in the low-risk category on the Bayley Infant Neurodevelopmental Screener (BINS), score a greater than 85 on all sub-scales of the Bayley Scale of Infant Development (BSID-II), have no history of significant cardiac, orthopedic, or neurological condition, and gestational age at least 37 weeks. Infants at risk for neuromotor delay will be at least 3 months and less than 11 months of age (corrected for preterm birth if applicable), score in the moderate or high risk categories on the BINS, and score an 85 or less on the motor sub-scales of the Bayley Scale of Infant Development (BSID-II). In an effort to decrease variability of the data, infants in each group will be further stratified into an older group (8-10+ months) and a younger group (3-5 months).

Study duration

1) We estimate that it will take two years from the date of IRB approval to enroll all subjects and complete the study. 2) At minimum, some subjects may be asked to experienced the Gym 1x. At most, a subject will be asked to use the Gym for up to 5 consecutive days. Each day the infant will use the gym, both with and without toys, for 3 minutes. 3) 5/01/2015 - 8/01/2017

Characteristics of the Study Population

Target population

Two populations will be involved: 1. Infants exhibiting typical development between 3 months and 11 months of age 2 . Infants exhibiting atypical development (at-risk for neuromotor delay) between 3 months and 11 months of age.

Subjects enrolled by Penn Researchers

50

Subjects enrolled by Collaborating Researchers

0

Vulnerable Populations **Children Form**

Pregnant women (if the study procedures may affect the condition of the pregnant woman or fetus) Form

Fetuses and/or Neonates Form

Prisoners Form

Other

None of the above populations are included in the research study

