
The following documents are currently attached to this item:

There are no documents attached for this item.

Deception

Does your project use deception?

No

International Research

Are you conducting research outside of the United States?

No

Analysis Plan

We will identify a battery of metrics derived from kinematic and kinetic measurements of infant movement that are able to discriminate between atypical and typical infants and evaluate neuromotor impairments. Metrics quantifying one and two-handed reach and grasp actions as well as leg and body actions will be derived from the data. We will also determine the reliability/reproducibility of our methods across the repeated measurements taken in the home. We also will examine how each metric correlates with the BINS and BSITDIII scores. The key primary metrics are unimanual and bimanual arm use, leg use, grasp forces, arm position when being used, and arm velocity when used. Secondary measures will be center of pressure from starting position, toy speed, toy acceleration, toy tilt angle, arm synchronicity, leg synchronicity, leg distance to toy, and respective differences in the percentage of arm use for reaching and for grasping. Given our long-term goal of detecting the emergence or lack of emergence of multiple milestones in the development of infants, we will examine a variety of metrics. Some of these milestones are the emergence of hand dominance using the relationship between the right and left hands; the emergence of unimanual or bimanual reaching using the relationship of the hand position to the toy, the hand speed, the frequency of movements; the emergence of unimanual grasping using grasping forces, the emergence of undifferentiated bimanual grasping detected by monitoring when the right and left arms start to move together toward a toy, and the emergence of differentiated bimanual grasping. For each variable, we anticipate having 120 data points per second for a minimum of 180 seconds. Initially, kinetic metrics, and frequency of reaching and grasping will be summarized using means and standard deviations each day, to assess for variability. Intraclass correlations coefficients (ICC) will be calculated to examine reliability/reproducibility of each measurement over the 5 days. If the ICCs are relatively high (.9), we will average the 5 days to create a single summary figure for each measurement to test. Using these summary figures, we will first perform 2-sample t-tests or Wilcoxon rank sum tests on the averages or ranks of each metric respectively, where the two groups represent atypical and typical infants, stratified by age group. Given our stratified groups of younger/older and typical/atypical infants, we anticipate having relatively large differences across most measures. Should the ICCs be low, due to learning we will use a 2-factor ANOVA in repeated measures where day would be the repeated measure and age group and infant type would be the 2 factors. For non-normal distributions, such as many zeroes for the atypical group or other non-normal/skewed distribution, we will use either Poisson (log-linear) regression or a Negative Binomial (ZINB) regression. All analyses will be performed using SAS statistical software. As we are looking for proof of concept, we will be looking for relatively large differences between atypical and typical babies. In order to build a machine algorithm to analyze the baby data, we will build a test data set from publically held YouTube videos. We will pull YouTube videos from babies between the ages of 1 month and 12 months.

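### Age is controlled only by two bands in non-randomised groups, so a systematic age gap within bands would confound the typical versus at-risk comparison, and within-band age variance stays in the error term

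*Combined protocol and SAP*

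**What the plan says.** Part B recruits 24 infants, "including 12 who are developing typically and 12 who are identified as at-risk for neuromotor delay" (Study Design, Design). The at-risk infants must be "at least 3 months and less than 11 months of age (corrected for preterm birth if applicable"; the typical infants have the same age limits and "gestational age at least 37 weeks". On the age bands, the section states: "infants in each group will be further stratified into an older group (8-10+ months) and a younger group (3-5 months". The reason that it gives for them is "In an effort to decrease variability of the data".

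In the Analysis Plan the first step is that "we will first perform 2-sample t-tests or Wilcoxon rank sum tests" on each metric, "where the two groups represent atypical and typical infants, stratified by age group". If reliability over the five days is low, a repeated-measures ANOVA replaces this, in which "day would be the repeated measure and age group and infant type would be the 2 factors". Poisson or negative binomial models are offered for skewed or zero-heavy metrics, with no covariates named.

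No analysis contains age as a continuous term, and no section describes age matching within bands. Under Subject recruitment, typical infants come from siblings of hospital patients and local parent groups. At-risk infants come mainly from a neonatal follow-up clinic, and also from a rehabilitation centre.

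**The concern.** The Analysis Plan treats reaching, grasping and hand dominance as milestones that emerge over the ages studied, so age probably predicts the metrics inside a band as well as between bands. The younger band covers two months or three, depending on whether its upper limit means the fifth month completed or begun. The older band, capped by the eligibility limit, covers close to three.

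Two consequences follow:

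- **Confounding.** If one group tends to be younger within a band, part of the group difference is age. Depending on direction, a metric could be credited with discriminating atypical development when it partly reflects age, or a real difference could be masked.
- **Precision.** Age-related variance within a band stays in the error term, which works against the stated purpose of the bands.

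Both could be reduced with data already in hand. Age must be known to judge eligibility and assign a band. Preterm correction is specified for the at-risk group, and the typical infants are term-born. That a usable corrected age exists for every infant is therefore a sound inference, although the plan does not state it.

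**Working it through.** The plan gives no alpha, effect size, SD or power, so there is no figure to reproduce.

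**Inputs.** From the Design section: 12 typical and 12 at-risk infants, and bands 2 to 3 months wide. Assumed: 6 infants per cell, ages uniform within a band, within-cell SD of 1, two-sided alpha of 0.05. The share of within-cell variance explained by age (R²) is also assumed, and is ranged from 0 to 0.5.

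**1. Chance imbalance in age.**
- Age SD in a band of width w is w/√12, which is 0.58 month (w = 2) or 0.87 month (w = 3).
- The SD of the 6 v 6 difference in mean age is that value × √(2/6), which is 0.33 or 0.50 month.
- By simulation, the difference exceeds half a month in about 14% (2-month) to 32% (3-month) of bands.
- At R² = 0.25, a half-month gap shifts that trial's estimate by (0.5/0.87) × √0.25 = 0.29 SD (3-month) or (0.5/0.58) × √0.25 = 0.43 SD (2-month).
- Averaged over such imbalances (40,000 simulated trials per setting), the band-only analysis has bias of about 0 and type I error of 4.9% to 5.2%.

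**2. Systematic gap of half an age SD within bands** (0.29 to 0.43 month).
- Bias of the band-only estimate = 0.5 × √R².
- Standard error in the two-factor model = √(2/12) = 0.408, with 20 df. Bias divided by standard error is the noncentrality, from which the type I error follows.

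| R² | Bias (SD) | Noncentrality | Type I error, bands only | Type I error, age added |
|---|---|---|---|---|
| 0.10 | 0.16 | 0.39 | about 6.5% | 5% |
| 0.25 | 0.25 | 0.61 | about 9% | 5% |
| 0.50 | 0.35 | 0.87 | about 13% | 5% |

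Simulation agrees, and with age in the model the bias is about 0. If the gap runs against a true difference of 1.0 SD, simulated two-factor power without age falls from 64% with no gap to 50%, 42% or 33%. With age in the model it is 64%, 71% or 87%.

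**3. Power with no systematic gap.** A true difference of 1.2 SD is used because it is what 12 v 12 detects with 80% power (6 v 6 needs 1.80 SD). Power comes from the noncentral t:
- Unadjusted: noncentrality d√(n/2), 2n − 2 df.
- Age-adjusted: noncentrality [d/√(1 − R²)] × √{(n/2)/[1 + 1/(2n − 4)]}, 2n − 3 df.

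| | No age term | R² 0 | 0.1 | 0.2 | 0.3 | 0.5 |
|---|---|---|---|---|---|---|
| 12 v 12 | 80% | 78% | 82% | 86% | 90% | 97% |
| 6 v 6 | 47% | 42% | 45% | 50% | 55% | 69% |

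Adding the age-group term to the 12 v 12 model changes these by less than one point. Break-even R² is about 0.05 at 12 v 12 and about 0.13 to 0.15 at 6 v 6.

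**The case against.** A reader might infer that chance age differences within such small cells bias the comparison. They do not. They shift the estimate in a particular trial, but the planned test's standard error already allows for this, and step 1 shows no average bias and nominal type I error. Bias needs a systematic gap. The documents make one possible, through non-random groups from different sources, but do not show that one exists.

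A reader might also infer that leaving out continuous age must cost power. The documents give no association between age and any metric, so that too is conditional. At 6 v 6 with weak association, adjustment costs up to about 5 points. This part of the objection stands, and it is why the covariate belongs in a pooled model and not in separate tests within each band.

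Further points have some force:

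- The no-toy recording is used to adjust for each infant's baseline activity, and hanging toys are placed relative to reach (Study Procedures). Both may absorb some age-related differences in activity and size. Neither removes age-related skill.
- A linear model for every metric would ignore the planned rank and count analyses, and a common age slope is doubtful if at-risk infants sit at a floor. The remedy must respect both.
- This is proof of concept, seeking large differences, and it already stratifies on age. That limits the weight of the point without removing it, because step 2 shows that a modest age gap can produce a bias of up to about a third of an SD.

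**Conclusion.** The concern holds as possible residual confounding by age within bands, together with age variance left in the error term. For a systematic gap of half an age SD, the bias is 0.16 to 0.35 SD and type I error about 6.5% to 13% over R² of 0.1 to 0.5. Both return to nominal when age is in the model. Without such a gap, the effect on 12 v 12 power runs from a loss of about 2 points (R² = 0) to a gain of about 17 (R² = 0.5). These sizes rest on an assumed R², an assumed even split of 6 per cell, uniform ages within bands, a linear age effect and an assumed alpha of 0.05.

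The eligible infants who fall between the two bands are a separate inconsistency. It concerns who is recruited and how they are classified, and an age covariate does not resolve it.

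**What to change.** In the Analysis Plan:

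- Prespecify continuous age in months (corrected where preterm), centred within age band, as a covariate in a model with infant type and age group, fitted to all Part B infants.
- Carry the same covariate into the repeated-measures model, and into the Poisson or negative binomial models where those are used.
- Keep the planned age-stratified t-tests or rank tests alongside the adjusted comparison.
- Report the age distribution by group and band, so that any gap is visible.
- Add a sensitivity analysis that checks the linear age slope and whether it is common to both groups.

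Separately, reconcile the eligibility range of 3 to under 11 months with the two bands in the Design section, which give no place to ages between them.

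**Cost.** The variable should already be held for every infant, so no new data are needed. The change does add an adjusted comparison to the planned ones, so the plan should say which of them leads. The statistical price is one degree of freedom, about 2 points of power at 12 v 12 if age is unrelated to the metric, plus the common-slope assumption.

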Prior to being assessed by the therapist, the parent or legal guardian will be consented. They will also be asked to fill out general surveys including, a demographic survey, and a case report form, and a user feedback survey which provides relevant information, on both the family's and infant's medical history and experience. After being assessed by a certified therapist for approximately one hour, both atypical and typical infants will be observed playing within the Gym. The environment will be prepared such that only items safe for infants will be in the testing and play areas. For the usability: The caregiver may be asked to closely observe and examine the hardware and the software of the system. The caregiver may then offer the toy to the infant for familiarization, observe the infant play and capture and upload a video of this interaction. The caregiver may be asked to complete a feedback and observation survey that will provide relevant information about the interaction and software and hardware experience. Part A) Data quantifying infants actions with and without toys will be collected in one or two sessions. Infants will be tested for their reaction to the gym without toys and then their reactions with 1 or multiple toys. The baby will be placed in the center of the gym. The baby will be allowed to settle and play for 1 minute then data will be collected again for 1-3 minutes. Each session will be recorded using the Microsoft Kinect camera. Arm/hand/leg position data will be collected with the Kinect camera, grasp pressure and forces will be collected, toy position and angular data will be collected via Kinect and inertial sensors, and central pressure data will be collected via the novel mat. Video data mapping their reaction may be collected using "Autism and Beyond" developed for research by Duke University. Part B) Data quantifying infant actions will be collected for 5 consecutive days under two conditions: with toys and without toys (control); the no toys condition will be tested first and the toy condition immediately after. The data from the no toy condition will be used to adjust the observations in the toy condition and will be used to account for the infants baseline actions per day. A test session will proceed as follows: First, the infant will be placed on his or her back at a pre-determined position on the gym mat in the no toy condition. Data will be collected for 3 minutes. The infant will be removed. The toys will be placed in the gym and adjusted for the infant reach; hanging toys will be placed at about 75% of the infants reach. After, the infant will be placed again with respect to the pre-determined position. To detect an infants intentional movement toward a specific toy, the location of each toy will be randomized within possible locations per toy type. The baby will be allowed to settle and play for 1 minute then data will be collected again for 1-3 minutes. Each session will be recorded using the Microsoft Kinect camera. Arm/hand/leg position data will be collected with the Kinect camera, grasp pressure and forces will be collected, toy position and angular data will be collected via Kinect and inertial sensors, and central pressure data will be collected via a pressure mat. General Procedure: A caregiver or parent will be seated at the head of the baby (out of baby's sight) to provide comfort if needed. Infants will be required to be alert and unhampered by clothing with their limbs free to move. They will be placed on their backs and allowed to roll or crawl as long as they stay within the perimeter of the device. If infants become frustrated (cries and is unsettled), the parent will be asked to pick them up and calm them. The trial will be restarted. If several attempts are unsuccessful, the session will be ended and attempted later in the day. We will take precautions to minimize the likelihood of participants experiencing any injury or discomfort. To avoid bumps, bruises or crashing into toys, participants will be supervised at all times by a trained study team member during CHOP sessions, including by a licensed pediatric physical therapist during developmental evaluations, and caregivers will be trained to place infants on their backs during home Gym play sessions. Caregivers will also be able to reposition their infants if he or she is uncomfortable.

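### Part B states a one-minute settling period before the toy data but none before the no-toy control used to adjust them

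*Combined protocol and SAP*

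**What the plan says.** All of this is in the Combined protocol and SAP. The session sequence is in Study Procedures, Procedures, Part B.

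- **Order:** "the no toys condition will be tested first and the toy condition immediately after", on each of five consecutive days.
- **Role of the control:** "The data from the no toy condition will be used to adjust the observations in the toy condition". It also stands for the infant's baseline actions on that day.
- **No-toy condition:** "First, the infant will be placed on his or her back at a pre-determined position on the gym mat in the no toy condition". The next words are "Data will be collected for 3 minutes. The infant will be removed". No settling period is mentioned.
- **Toy condition:** the toys are hung, and then "After, the infant will be placed again with respect to the pre-determined position". After that, "The baby will be allowed to settle and play for 1 minute then data will be collected again for 1-3 minutes".

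The Analysis Plan says of each variable that "we anticipate having 120 data points per second for a minimum of 180 seconds". It does not say how the no-toy and toy windows are to be aligned, or how the adjustment is to be made. The Part A description also contains the settling sentence, but does not tie it to one condition; this point concerns Part B only.

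**The concern.** A baseline isolates the response to toys only if the two recordings differ in the toys and in as little else as possible. Here they also differ in time since placement. Both conditions begin with the infant being put down on the mat, but a settling minute is stated for only one of them. That the protocol allows such a minute at all suggests that settling is thought to affect the measurements.

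The order is fixed, so counterbalancing cannot offset the mismatch. It recurs every day, so averaging five days leaves a systematic shift in place. A shift that is stable within infants is compatible with a high ICC, so the reliability check would not reveal it. If settling shortens as infants get used to the gym, the shift would change from day to day and could be taken for learning.

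At stake is the toy-versus-baseline value for metrics that exist in both conditions, mainly arm and leg use. If the two groups settle differently, the typical versus at-risk comparison is affected as well.

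**Working it through.** The documents give no figure for settling and no calculation to reproduce. The check has two parts: set the two windows side by side, then see what the mismatch does under a stated assumption.

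**1. The windows as written** (times from Procedures, Part B; 120 points per second from the Analysis Plan)

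| | No-toy | Toy |
|---|---|---|
| Stated settling period | none | 1 min |
| Window after placement | minutes 0 to 3 | starts at minute 1, lasts 1 to 3 min |
| Seconds of data | 180 | 60 to 180 |
| Points | 120 × 180 = 21,600 | 7,200 to 21,600 |
| Share from minute 0 to 1 | 60/180 = one third | 0 |

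**2. Effect on the baseline.** Let s be the settled no-toy activity rate and f × s the rate in the first minute after placement. Assume that settling lasts no more than one minute. The range of f is an assumption.

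- Baseline as written: s(f + 1 + 1)/3 = s(f + 2)/3.
- Baseline from a settled window: s.
- Shift in toy minus baseline: s − s(f + 2)/3 = s(1 − f)/3.

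| f | Baseline ÷ settled value | Shift in toy minus baseline (units of s) |
|---|---|---|
| 0.5 | 0.83 | +0.17 |
| 1 | 1.00 | 0 |
| 1.5 | 1.17 | −0.17 |
| 2 | 1.33 | −0.33 |
| 3 | 1.67 | −0.67 |

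**3. Effect on the group contrast.** Under a difference adjustment, with the same settled rate s in both groups, the bias in at-risk minus typical is −s(f_risk − f_typ)/3.

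- f_risk = f_typ: bias 0, whatever the common value.
- f_typ = 1 and f_risk = 1.5, 2 or 3: bias −0.17, −0.33 or −0.67 of s.
- f_typ = 1 and f_risk = 0.5: bias +0.17 of s.

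The cancellation requires the settling excess, s(f − 1), to be equal in the two groups. If the settled rates differ, a common f other than 1 leaves a remainder of (1 − f)(s_risk − s_typ)/3.

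**4. After matching the windows.** If no-toy data also start at minute 1, the settled baseline is s and the shift is 0 for every f, provided settling is over within the minute. If it takes longer, both windows still start at the same time since placement.

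**5. The cheaper alternative.** Dropping minute 0 to 1 from the existing no-toy record leaves 180 − 60 = 120 s, or 120 × 120 = 14,400 points. That is below the 180 s minimum in the Analysis Plan.

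**The case against.** The case on the other side is substantial, and much of it limits the point.

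- **Start of recording.** A reader might infer that the control is recorded from the instant of placement. The protocol gives no start time, so an unwritten settling period cannot be excluded. What stands is that none is stated; if one is intended, it needs to be written down.
- **The first toy minute.** A reader might infer that the initial response to the toys is discarded or never recorded. The documents do not support this: Part B also says that every session is recorded with the Kinect camera, which supplies limb position data. The minute lies outside the stated data window, and no more can be said.
- **Bias is conditional.** The shift is zero at f = 1. An equal settling excess in both groups cancels in the group contrast under a difference adjustment, and the documents hold no evidence that the groups settle differently.
- **Few metrics are exposed.** Grasp force, toy speed, toy acceleration and toy tilt have little or no no-toy counterpart. Arm position and velocity are defined only while the arm is in use, so a rate model does not carry over to them directly.
- **Partial safeguard.** The General Procedure requires an alert infant and restarts the trial after crying. This limits overt distress in the control data, but not milder settling movement.
- **A defensible choice.** Letting infants get used to new toys before measuring is reasonable in a proof-of-concept study that looks for large differences. That explains a settling minute with toys, but not its absence before the control.

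**Conclusion.** The mismatch is in the text and nothing else in the document reconciles it. Followed as written, the daily baseline and the observations it adjusts come from different post-placement windows, in a fixed order. It should be put right before Part B testing, because a lead-in that was not allowed cannot be added to a recording afterwards.

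The size is illustrative. For f between 0.5 and 2 the baseline lies between 0.83 and 1.33 of its settled value, and the true f is unknown. The figure of 33% at f = 2 is inflation of the baseline mean. A reader might take it as the error in the typical versus at-risk comparison, but the documents do not support that: it would require, for example, f = 2 in one group and f = 1 in the other with equal settled rates. Because the Analysis Plan does not say whether the adjustment is a difference, a ratio or a covariate, the effect on the final comparison cannot be fixed.

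**What to change.** In Procedures, Part B, use the same sequence in both conditions: placement, a one-minute settling period, then data collection. In the Analysis Plan, state that baseline and toy metrics are taken from the same post-placement window, starting at minute 1. A common window of minutes 1 to 4 would meet the 180 s minimum. The present 1-to-3-minute toy recording can fall to 60 s, so its length needs reconciling with that minimum at the same time. The form of the adjustment should be named there too.

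The cost is about one extra no-toy minute per session. Time on the mat, now 3 + 1 + (1 to 3) = 5 to 7 minutes, becomes 4 + 1 + (1 to 3) = 6 to 8 minutes if the toy recording is left as it is. The daily gym time under Study duration, given as 3 minutes, must be updated to match.

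Excluding minute 0 to 1 of the no-toy record is only a fallback, because it leaves 120 s. Keeping the first toy minute as a separate measure of initial response is optional and not part of the correction. The fixed order of conditions is unchanged by this fix.

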Diagnostic test/procedure (research-related diagnostic test or procedure)

Obtaining human tissue for basic research or biospecimen bank

Survey instrument

None of the above

The following documents are currently attached to this item:

There are no documents attached for this item.

Department budget code

None

Protocol**Objectives****Overall objectives**

We aim to develop a Gym where sensitized, wireless toys are strategically hung and placed within reach of infants to elicit toy-oriented body and arm/hand movements. Each toy will be equipped with sensors capable of measuring the infant's grasping actions such as squeezing, pinching, tilting, etc. A low-cost 3D motion capture system will be used to collect video data and the infants' reaching and body kinematics in response to the toys. A pressure mat will be used to measure postural changes to detect weight shifts, rolling, crawling and other movements away from the initial posture. By capitalizing on these wireless and low-cost technologies, it will permit the regular and non-invasive monitoring of infants, which can lead to detailed, non-obtrusive, quantitative evaluation of motor development. In this vein, we also aim to conduct proof-of-concept testing of the Gym with atypical and typical developing infants. We will include infants' ages 3 to 11 months who are categorized as high-risk or low-risk using the Bayley Infant Neurodevelopmental Screener.

Background

An estimated 5 to 10 percent of children have developmental disabilities (Rydz 2005), and an increase in survival rates of medically fragile infants has led to an increased number of children with functional impairments later in life (Vohr et al 2003). Particularly, pre-term and low birth weight infants as well as those exposed to brain injuries due to a central nervous injury insults such as asphyxia, neonatal seizures, prenatal drug use, or maternal infections are at increased risk for developmental delays and neurologic impairment. Successful early detection of delay or impairment in at-risk infants depends on the effectiveness of standard clinical scales, many of which are not sufficiently sensitive to screen infants younger than 6 months (Leonard et al 2001). For example, one popular scale was reported to have a positive predictive value of 67 percent for motor or cognitive impairment, i.e., high risk infants identified at 6 months using the screening tool were 67 percent likely to have a cognitive impairment at

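### Part B records the toy condition for 1-3 minutes, but the Analysis Plan anticipates at least 180 seconds per variable, and counts and the no-toy adjustment have no stated time scale

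*Combined protocol and SAP*

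**What the plan says.** Three places in the combined protocol and SAP bear on recording length.

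- **Study Procedures, Procedures, Part B.** The no-toy condition comes first: "Data will be collected for 3 minutes. The infant will be removed". The toys are then placed, and the toy condition follows: "per toy type. The baby will be allowed to settle and play for 1 minute then data will be collected again for 1-3 minutes". Nothing says what decides between 1 and 3 minutes. On the use of the control recording: "The data from the no toy condition will be used to adjust the observations in the toy condition". No formula or time scaling is given.
- **Analysis Plan.** For each variable, "we anticipate having 120 data points per second for a minimum of 180 seconds". The next sentence turns to daily summaries: "frequency of reaching and grasping will be summarized using means and standard deviations each day". Frequency has no unit. The Poisson and negative binomial models offered for non-normal data have no stated offset.
- **Study duration.** Infants use the gym with and without toys for 3 minutes each day. This describes use rather than recording, so it is weaker evidence.

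Two further statements identify the variables affected. The Overall objectives put the grasp sensors in the toys: "Each toy will be equipped with sensors capable of measuring the infant's grasping actions". The Analysis Plan then says "The key primary metrics are unimanual and bimanual arm use, leg use, grasp forces", among others, and lists "toy speed, toy acceleration, toy tilt angle" among the secondary measures.

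**The concern.** For the toy recording, the minimum in the Analysis Plan equals the maximum in the procedure. Two things follow.

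First, the anticipated amount of data is not guaranteed for variables that can be measured only when toys are present. One of these is a key primary metric.

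Second, the planned adjustment sets a 1-3 minute recording against a 3-minute one. A metric analysed as a raw count or total would then reflect recording time as well as behaviour. An infant whose movement did not change could appear to move less with toys. This needs no difference in windows between the groups, because the unequal windows are written into the procedure. Raw counts of toy-only events, such as grasps, have no no-toy counterpart, but they could still vary up to threefold from day to day with the window alone.

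**Working it through.** **Inputs from the documents.** Sampling at 120 points per second for at least 180 s (Analysis Plan); no-toy window 3 min; toy window T = 1 to 3 min after 1 min of settling; 5 consecutive days (Procedures, Part B).

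**Step 1: the plan's own figure.** 120 x 180 = 21,600 points per variable.

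**Step 2: what the toy window supplies per day.**

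| Toy window | Points | Share of 21,600 |
|---|---|---|
| 60 s | 120 x 60 = 7,200 | 33% |
| 120 s | 120 x 120 = 14,400 | 67% |
| 180 s | 120 x 180 = 21,600 | 100% |

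**Step 3: which readings reach 180 s at the shortest window.**

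- No-toy recording alone: 180 s. Met for variables measured in both conditions.
- No-toy plus toy within a day: 180 + 60 = 240 s. Met for the same variables.
- Toy recording plus the settling minute: 60 + 60 = 120 s. Not met.
- Toy recording over 5 days: 5 x 60 = 300 s. Met, but only if the 180 s is not a daily figure.

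The shortfall therefore concerns toy-only variables, with the 180 s read as daily.

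**Step 4: scale of the no-toy adjustment for raw counts.** With the same rate r per minute in both conditions, the toy/no-toy ratio is rT/(3r) = T/3: 0.33 at 1 min, 0.67 at 2 min, 1.00 at 3 min. A raw toy-minus-no-toy difference is expected to be negative unless the toy rate exceeds 3/T times the no-toy rate: 3 times at 1 min, 1.5 times at 2 min. No event rate has to be assumed.

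**Step 5: illustrations under assumed inputs.** The documents give no event rates, between-infant variation or window distribution. Assumed here: between-infant CV 0.5 and windows drawn uniformly and alike in both groups.

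*Power.* 6 v 6 infants (12 per group, assumed to split evenly by age stratum), gamma infant rates with the same infant factor in both conditions, Poisson counts, 5-day means, two-sided 5% t-test, 40,000 simulated trials per cell. The adjustment is taken as raw subtraction of the no-toy count. No-toy/toy rates per minute are 1/2 (at-risk) and 2/4 (typical).

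| Toy window | Raw counts | Per-minute rates |
|---|---|---|
| Fixed 3 min | about 36-37% | same |
| 1-3 min | about 12% | about 32% |
| 2-3 min | about 27-28% | about 35% |

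If instead no-toy rates are equal (2/min) and only typical infants double with toys, power goes from 97% (fixed) to 91% (1-3 min; rates 94%). Type I error stays near 5%.

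*ICC of counts.* At 4 events/min and CV 0.5, the rate variance is 4. With window mean m and variance v, between-infant variance = 4m² and within-infant variance = 4m + 20v. The single-day ICC is between/(between + within); for the 5-day mean, within is divided by 5.

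- Fixed 3 min: 36 and 12, so 0.75; 5-day 36/(36 + 2.4) = 0.94.
- 1-3 min (m = 2, v = 1/3): 16 and 14.67, so 0.52; 5-day 0.85.
- 2-3 min (m = 2.5, v = 1/12): 25 and 11.67, so 0.68; 5-day 0.915.
- Per-minute rates, 1-3 min: within = 4 x ln(3)/2 = 2.20, so 4/6.20 = 0.65; 5-day 4/4.44 = 0.90.

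**The case against.** The 180 seconds is worded as an expectation for each variable, not as a requirement per condition or per day. The no-toy window alone supplies it for most variables, and five days of toy recording supply it for the rest. This stands in part: the daily reading is an interpretation, though a reasonable one because daily summaries follow directly.

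Few metrics are clearly exposed. Grasp force, arm position and arm velocity are levels, which do not scale with recording time unless totalled. Arm and leg use are undefined, and a secondary measure expresses arm use as a percentage. Frequency often means events per unit time. This stands: a reader might infer that the sponsor plans to analyse raw counts, but the documents show only that the unit is not stated.

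A reader might also infer a biased group comparison. In an assumed case (12 v 12, 5 events/min, CV 0.5, equal true rates), false positives for raw counts are about 12% with 2.5 v 3 minutes and 44% with 2 v 3 minutes. Windows varying alike over 1-3 minutes in both groups give about 5%. The restart rule for frustrated infants makes unequal usable time plausible, but the documents neither show nor exclude a group difference.

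Finally, Part B's sentence repeats Part A's word for word, so it may be a carry-over. Correcting it would settle most of the point. That is a reason to correct it, since the text as it stands gives unequal windows.

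**Conclusion.** The plan is wrong as written on recording length, with low to moderate severity. The firm part is textual: a 1-3 minute toy window, a fixed 3-minute control window used to adjust it, and an anticipated 180-second minimum. For toy-only variables, 7,200 points a day are guaranteed against 21,600, on the daily reading. The mis-scaling of 0.33 to 1.00 follows by arithmetic for any metric recorded in both conditions and analysed as a raw count or total. Levels and percentages lose precision only.

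The power, ICC and false-positive figures are illustrations and depend strongly on the assumed windows, as the 12% against 27-28% power shows. A lower ICC caused by varying windows could be mistaken for learning, the only cause the plan names. A reader might infer that this spoils the group test, but in balanced data the fallback repeated-measures ANOVA compares infant types on the same 5-day means.

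**What to change.** 1. Reconcile the recording length across Study duration, Procedures (Part B) and Analysis Plan, or restate the 180-second minimum for toy-only variables. If Part B's range was carried over from Part A, correcting it is enough for complete recordings.
2. If the window stays variable, say what ends a recording and record usable seconds per condition and day. Analyse counts and totals per usable minute, with log(usable minutes) as an offset in the Poisson and negative binomial models. Apply the no-toy adjustment on the same per-minute scale.

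The cost is wording plus, at most, one field per condition per day. Since the sampling rate is known, recorded length can be derived from the sample count, leaving only unusable time to flag. The downside is that rates from short windows are noisier than rates from a fixed 3 minutes (5-day ICC 0.90 against 0.94 in the illustration). Per-minute scaling corrects the scale but does not recover lost recording time.
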